1 BACKGROUND

1.1 Common Warts

Verruca vulgaris, common warts, are caused by the human papilloma virus (HPV). HPV infects epithelial cells and, in the case of common warts, cause proliferation of the fully differentiated epithelium resulting in clinically evident warty papules. Most authors agree that the prevalence of non-genital warts is between 7 and 10% in the US. Young people are preferentially affected, with the peak incidence being reported between the ages of 12 and 16 years. Common warts are least common among infants and the elderly.¹⁻⁷ Common warts occur most frequently on hands and feet, less frequently on limbs, torso or face where flat warts are more common.^{5,7} New common warts frequently regress spontaneously with reports of roughly 60% regressing within two years, and roughly 30% of subjects experiencing spontaneous regression of at least one wart during a nine month period.^{1,2,7,8} However, the remaining roughly 40% may remain for years. While many subjects are instructed to wait and see if the warts resolve spontaneously, warts can bleed, itch, be painful and disfiguring, with 52% of subjects experiencing moderate to severe discomfort and 81% being moderately to extremely embarrassed by the presence of their warts.⁷ Additionally, untreated warts serves as a reservoir for continued shedding of contagious papilloma virus.

1.2 Treating Common Warts

[figure not shown]

1.3 Candida Albicans Skin Test Antigen for Cellular Hypersensitivity (Candin®)

CANDIN is currently marketed in the United States indicated for use as a recall antigen for detecting DTH by intradermal injection of 0.1 mL. The product may be useful in assessing the cellular immune response in individuals suspected as having decreased immune responses of this type, such as those with AIDS, HIV, and cancer. Local reactions observed in the development of CANDIN for DTH included redness, swelling, pruritus, vesiculation, weeping edema, excoriation, induration, and discoloration of the skin. Immediate hypersensitivity has been observed within 20 minutes of injection characterized as an edematous hive with a surrounding zone of erythema. Up to approximately 20% of subjects had lesions of 10-24 mm diameter and another group of up to approximately 13% had lesions of less than 10 mm diameter.

1.4 CANDIN for the Treatment of Common Warts

2 STUDY HYPOTHESIS AND OBJECTIVE(S)

Hypothesis:

The null hypothesis for this study is that the CANDIN treatments are not significantly different from placebo under these experimental conditions

Objective(s):

The primary objective is to assess the efficacy of CANDIN treatment in subjects with common warts by evaluating the number and proportion of subjects with the primary injected wart(s) completely resolved.

The secondary objectives are:

1. To assess the safety and tolerability of CANDIN

[figure not shown]
3 STUDY ENDPOINTS

3.1 Primary Endpoint

The number and proportion of subjects with the primary injected wart(s) completely resolved at any treatment or Follow-up Visit.

3.2 Secondary Endpoints

1. Incidence of site injection AE for all subjects and TEAE for subjects randomized to CANDIN

Protocol Final version 5.0: 06Dec2016

4 STUDY DESIGN

This is a placebo-controlled, double-blind (subject, Investigator, and site staff with the exception of unblinded dedicated staff to handle study medication), phase 2a study with 3 dose cohorts, randomized (concealed) to CANDIN or placebo (3:1). Main study will be up to 20 weeks (10 doses administered every other week) or until a subject has complete resolution of all injected common warts. Subjects who cannot tolerate dosing every 2 weeks due to a local tolerance issue may be injected at 3-week intervals for up to 10 doses, increasing the length of the study to 29 weeks (+/- study windows). Subjects will be followed for 4 months after final injection(s) for evidence of new or reoccurring warts and for safety evaluation.

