Hypersensitivity) or Placebo administered intralesionally in the largest common

wart

Cohort 2: 0.5 mL of CANDIN or Placebo administered intralesionally in the

largest common wart

Cohort 3: 0.3 mL of CANDIN or Placebo administered intralesionally in up to 4

warts at the same visit (up to 1.2 mL total injected volume)

Population: Approximately 156, male or female subjects aged 18 to 65, with 3 to 20 common

warts on hands, feet (excluding soles), limbs and/or trunk will be included in this

study

Number of Sites: Approximately 15 centers in USA will participate in this study

Study Duration: Subjects will be treated for a maximum of 29 weeks followed by a 16-week

observation period for a total of 45 weeks, excluding the 4-week screening period.

Hypothesis: The null hypothesis for this study is that the CANDIN treatments are not

significantly different from placebo under these experimental conditions

Objectives:

The primary objective is to assess the efficacy of CANDIN treatment in subjects with common warts by evaluating the number and proportion of subjects with the primary injected wart(s) completely resolved.

The secondary objectives are:

1. To assess the safety and tolerability of CANDIN

Nielsen- CFW-2D Protocol Final version 5.0: 06Dec2016

Endpoints:

[figure not shown]
Primary Endpoint:

 The number and proportion of subjects with the primary injected wart(s) completely resolved at any treatment or Follow-up Visit

Secondary Endpoints:

1. Incidence of site injection Adverse Event (AE) for all subjects and Treatment-Emergent Adverse Event (TEAE) for subjects randomized to CANDIN

Overall Study Design

This is a placebo-controlled, double-blind (subject, Investigator, and site staff with the exception of unblinded dedicated staff to handle study medication), phase 2a study with 3 dose cohorts, randomized (concealed) to CANDIN or placebo (3:1). Main study will be up to 20 weeks (10 doses administered every other week) or until a subject has complete resolution of all injectable common warts. Subjects who cannot tolerate dosing every 2 weeks due to a local tolerance issue may be injected at 3-week intervals for up to 10 doses, increasing the length of the study to 29 weeks. Subjects will be followed for 4 months after final injection(s) for evidence of new or reoccurring warts and for safety evaluation.

Inclusion Criteria

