6 TREATMENT

6.1 Treatment Administered

Subjects who fulfill all the inclusion and none of the exclusion criteria may be accepted in the study. Each subject should read and sign an informed consent form prior to any screening procedures being performed. This study involves a comparison of an intralesional injection of CANDIN with an intralesional injection of placebo (unpreserved normal saline solution) in common warts. Subjects will receive one (Cohorts 1 and 2) or more (Cohort 3) intralesional injections every two weeks (14 +/- 2 days) at the region of the interdigitated base of wart (epidermal/dermal junction) for up to 20 weeks (a maximum of 10 doses per subject) or up to resolution of all injectable warts. Subjects who experience local tolerance issues when dosing is performed at 2-week intervals may be injected at 3-week intervals (21 +/- 2 days) also for a maximum of 10 doses per subject.

Subjects will be included in three cohorts as follows:

- 1. Cohort 1: Approximately 52 subjects will receive 0.3 mL of either CANDIN (n=39) or placebo (n=13) intralesionally in the largest common wart (primary) every second week (14 +/- 2 days) for a maximum of 10 injections. If the primary common wart exhibits a complete response, the second largest injectable common wart of all anatomical regions will be injected with CANDIN at the same dose. If the second largest common wart exhibits a complete response, the third largest of all anatomical regions will be injected. If an injected wart recurs after exhibiting a complete response, it will be re-injected instead of the non-primary injected wart that was injected at the previous visit. This injection strategy will be repeated for a maximum of 10 injections per subject or until all injectable common warts exhibit a complete response, if it occurs before all 10 injections are used.
- 2. **Cohort 2:** Approximately 52 subjects will receive 0.5 mL of either CANDIN (n=39) or placebo (n=13) intralesionally in the largest common wart every second week (14 +/- 2 days) for a maximum of 10 injections. If the primary common wart exhibits a complete

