8.1.1 Common wart measurement

The visually largest six common warts (including the primary injectable wart(s)) that can be readily identified will be measured at Baseline Visit (V3) and during the study (referred as "measured warts"). Unless the wart location can be easily identified in writing using anatomical terms, these (up to 6) largest common injectable warts will be mapped on transparencies or drawn in the medical chart to ensure it is accurately found at every visit. The mapping process on transparencies will be described in the Study Manual.

Each measured wart will be documented in the source document and reported on the eCRF, with its size, age, treatment history and location. Size will be determined by measuring in mm the longest and orthogonal diameters of the wart using a ruler.

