- 2. If the medical Investigator deems appropriate because of tolerance issues the injection schema may be changed to every 3 weeks instead of 2 weeks for a maximum of 10 doses.
- 3. Female of childbearing potential only. Serum pregnancy at screening and urine pregnancy test at other visits.
- 4. At selected sites, for a maximum of 10 subjects per cohort.
- 5. Post 48h of DTH injection from V1.
- 6. Cohort 1 only.
- 7. DTH Diary
- 8. Applicable only if there is complete resolution of the primary injected wart(s).
- 9. One for Cohort 1 and 2; and up to 4 in Cohort 3.
- 10. If complete resolution of all common warts, not just the primary injected wart(s), is observed at any of the visits following Baseline, the procedures described under Visit 13 will be performed. This visit also will be performed in the event of an early termination.
- 11. To be initially assessed at Visit 3 and prior to the first injection in case of selection and mapping of non-primary common wart(s) for injection (V4 to V12). To be re-assessed at the site of resolved primary and non-primary injected wart(s) must be recorded as an AE if at Baseline (V3), or prior to the first injection in case of selection and mapping of non-primary common wart(s) for injection (V4 to V12) it was assessed as absent.
- 12. Prior to injection.
- 13. On certain occasions, administering the DTH challenge at V1 may result in a difficulty scheduling V2 at the 48 hour time required (for example V1 on a Thursday or Friday resulting in V2 on a weekend). The investigator may perform the DTH challenge on an additional visit after V1 (subvisit) in order to schedule an acceptable V2, provided the DTH challenge is performed within 1 week of V1 and a urine pregnancy test is performed if required for a given subject. Urine pregnancy testing not required for women of non-childbearing potential defined as post-menopausal for at least 2 years or surgically sterile (tubal ligation, oophorectomy, or hysterectomy).
- 14. V1 and V13 should not be scheduled on a weekend if at all possible due to shipping restrictions of blood samples.

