6 STUDY SUBJECTS

6.1 Subject Disposition

Subject disposition information, including the number and percent of subjects who completed treatment, discontinued treatment further broken down by primary reason for treatment discontinuation, subjects who completed the study and terminated early from the study further broken down by reason for early termination will be summarized by cohort and treatment for the Randomized population.

Subjects who completed treatment will be defined as those who completed all 10 injections, or with all injectable warts resolved by Efficacy Evaluation Visit (Visit 13). An injectable wart is defined as any measured wart.

Subjects who completed the study will be defined as those who completed treatment and both follow-up visits (Visit 14 and Visit 15).

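### End-of-injection wording, the V13 trigger and the SAP definition of an injectable wart do not agree, which affects disposition counts and follow-up timing but not the primary endpoint

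*Protocol*

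**What the plan says.** Four different states of the warts are used to mark the end of treatment or the move to follow-up.

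- **All injected warts.** Protocol 4 and the first paragraph of SAP 3.1 run the main study for up to 20 weeks or "until a subject has complete resolution of all injected common warts".
- **All injectable warts.** The Protocol synopsis has "until a subject has complete resolution of all injectable common warts". Protocol 6.1 gives injections for up to 20 weeks "or up to resolution of all injectable warts", and its cohort text continues to the maximum of 10 or "until all injectable common warts exhibit a complete response". The cohort paragraphs of SAP 3.1 say the same.
- **All common warts.** SAP Table 1 footnote 10 calls for the V13 procedures "If complete resolution of all common warts, not just the primary injected wart(s), is observed at any of the visits following Baseline". The last paragraph of SAP 3.1 uses the same state for subjects who go to follow-up early. Protocol 8.1.2 defines it as a wart count of zero.
- **All measured warts.** SAP 6.1 counts treatment as completed after 10 injections, or when all injectable warts are resolved by V13. It then adds: "An injectable wart is defined as any measured wart". Protocol 8.1.1 limits these: "The visually largest six common warts (including the primary injectable wart(s)) that can be readily identified will be measured". Entry criterion 2 allows 3 to 20 injectable warts.

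**The concern.** These states are not interchangeable. A subject can have up to 20 injectable warts, of which six are measured. The same subject can also have common warts that may not be injected, for example because they fall outside 3 to 20 mm or lie in a tattooed or inflamed area (Protocol 5.1 criterion 3, Protocol 5.2 criterion 4).

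The end-of-injection rule and the V13 trigger fix the date of V13. V14 and V15 follow from it, at 4 and 16 weeks after V13 (SAP 3.2). They therefore set how long a responder is observed for TEAEs, which SAP 7.3.1 counts through V15, and for recurrence. The SAP 6.1 definition decides who is reported as having completed treatment. Completion of the study is built on completion of treatment, so it inherits any error.

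The problem arises only in subjects whose warts clear. The plan assumes more of these on an active arm (70%) than on placebo (24%), so any effect would not be spread evenly over the groups.

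**Working it through.** **1. The plan's own timetable.** Ten doses span nine intervals. At 2 weeks: 9 × 2 = week 18, + 2 = week 20. At 3 weeks: 9 × 3 = week 27, + 2 = week 29, + 16 = week 45. These match the stated 20, 29 and 45 weeks. The 2 weeks from last dose to V13 is an assumption that fits both schedules.

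**2. The rules side by side.**

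| Place | State required | What it governs |
|---|---|---|
| Protocol 4; SAP 3.1 opening | all injected warts | end of main study |
| Synopsis | all injectable warts | end of main study |
| Protocol 6.1; SAP 3.1 cohort text | all injectable warts, or 10 injections | injections |
| SAP Table 1 footnote 10; SAP 3.1 last paragraph | all common warts | V13 and early follow-up |
| SAP 6.1 | all measured warts (at most 6), or 10 injections | counted as completed treatment |

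**3. Injected against injectable.** In Cohorts 1 and 2 one wart is injected at a time. Read literally, the *injected* wording is satisfied when the primary wart clears. Protocol 6.1 then says: "If the primary common wart exhibits a complete response, the second largest injectable common wart of all anatomical regions will be injected". The two cannot both be applied. The detailed dosing text is consistent in using *injectable*.

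**4. The V13 gap.** Assume Cohort 1, 2-week dosing, *w* injectable warts each clearing after one injection, no recurrence, and one non-injectable common wart that persists. The last needed injection is at week 2(*w* − 1) and clearance is seen at week 2*w*. Footnote 10 is never met, so V13 stays at week 20. The alternative is V13 at the clearance visit. V15 is V13 + 16 weeks.

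| *w* | V13 at clearance | V13 as scheduled | Shift (weeks) | V15 | Weeks from last injection to V15 |
|---|---|---|---|---|---|
| 3 | 6 | 20 | 14 | 22 or 36 | 18 or 32 |
| 6 | 12 | 20 | 8 | 28 or 36 | 18 or 26 |
| 8 | 16 | 20 | 4 | 32 or 36 | 18 or 22 |
| 10 or more | 20 | 20 | 0 | 36 | 18 |

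With three warts needing two injections each, clearance is at week 12 (shift 8 weeks). With three injections each it is at week 18 (shift 2 weeks). With six or more warts needing at least two each, the maximum of 10 is reached first and the shift is nil.

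The trigger is also hard to apply. Common warts other than the measured ones are scheduled for evaluation at V3, V13, V14 and V15, and the full-body examination is at V3, V7, V13 and V15. At most of V4 to V12 the flow chart has no assessment covering all unmeasured warts, apart from selecting the next wart to inject.

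**5. The SAP 6.1 definition.** Up to 20 − 6 = 14 injectable warts can lie outside it. Under the same assumptions with *w* = 8, the six measured warts have cleared after 6 doses (week 12) and all injectable warts after 8 doses (week 16). A subject who stops at week 12 is two doses short under Protocol 6.1 but is a treatment completer in the SAP. If V14 and V15 are attended, the same subject is a study completer.

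The definitions agree when a subject has six or fewer injectable warts, all of them measured. They also agree once 10 injections have been given: at two injections per wart, 6 × 2 = 12 exceeds 10. SAP 6.3 meanwhile takes its compliance denominator from warts eligible under the Protocol, so adjacent SAP sections use two meanings.

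**6. Primary endpoint.** The primary wart(s) belong to the injected, injectable, measured and common sets alike. Whichever rule is met, they have already resolved, and the endpoint counts resolution at any treatment or follow-up visit.

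**The case against.** The strongest reply is that sites would follow Protocol 6.1. It sets out the move to the second and third wart, the SAP cohort text repeats it, and the flow charts schedule selection of non-primary warts at V4 to V12. Footnote 8 ties that step to resolution of the primary wart, and footnote 10 says clearance of the primary wart alone is not enough. This stands. A reader might infer from Protocol 4 that dosing stops when the primary wart clears, so that dose totals differ widely. The documents do not support that, because it would empty all of these provisions of meaning.

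Nor can the number affected be had by applying the assumed 70% resolution rate to the 39 active subjects of a cohort. The endpoint also counts resolution first seen at V13 to V15, when dosing is over, and the plan gives no timing.

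It is also fair that footnote 10 triggers a visit and does not end injections, so the gap concerns visit timing and not dose. SAP 6.1 likewise sits under subject disposition and does not govern dosing. Misclassification needs more than six injectable warts, early clearance of all six measured ones, and a stop before the tenth injection. Finally, most of Protocol section 7 and the notes to the Appendix A chart are not in the available text and may hold a V13 rule.

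None of this removes the two remaining conflicts: the visible text gives no V13 trigger when only a non-injectable common wart remains, and SAP 6.1 can class a subject still due injections as having completed treatment.

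**Conclusion.** The inconsistency is real but limited. The *injected* wording in Protocol 4 and SAP 3.1 contradicts the sequential rule and is probably a slip of summary. The V13 gap would move V13 to V15 by 0 to 14 weeks in the illustrations above, and with them the TEAE and recurrence window, without changing dosing. The SAP 6.1 definition can inflate the treatment-completed and study-completed counts in a narrow set of subjects.

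How many subjects fall into either group cannot be worked out from the documents, which give neither the distribution of wart counts nor the time to clearance. The illustrations assume a fixed number of injections per wart and no clearance of uninjected warts. They are examples, not bounds; in Cohort 3, with up to four warts injected per visit, the measured warts could clear sooner.

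The primary endpoint is unaffected. That none of the visible text supplies the missing V13 rule is subject to the parts of the Protocol that are not available.

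**What to change.** - Reconcile the Protocol synopsis, Protocol 4, Protocol 6.1, SAP 3.1 and SAP Table 1 footnote 10 to one end-of-injection rule and one V13 trigger. State what happens when all injectable warts have cleared but another common wart remains. Which rule applies is the sponsor's decision.
- In SAP 6.1, either delete the sentence equating injectable with measured, or report resolution of all measured warts as a separate category that does not by itself count as completed treatment. Use the same meaning of injectable in SAP 6.1 and SAP 6.3.

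The cost is a Protocol clarification and a SAP wording change. No new data, sample size or primary analysis is involved.

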5 STUDY POPULATION

Approximately 156, male or female subjects aged 18 to 65 inclusively at the signature of consent with 3 to 20 common warts on hands, feet (excluding soles), limbs and/or trunk will be included in this study in order to complete with approximately 115 subjects. Drop-outs will not be replaced. Additional subjects may be added to ensure approximately 115 subject complete the study in the event an investigator or site discontinues participation in the study

5.1 Inclusion Criteria

Subjects may be eligible if they meet all the following inclusion criteria at the Screening and Baseline Visits unless specified otherwise:

- 1. Men or women between the ages of 18 and 65 years inclusively at time of consent
- 2. Subjects presenting with 3 to 20 injectable common warts (verruca vulgaris) for at least 12 weeks at the time of the Baseline Visit
- 3. Subject's common warts for injection must measure between 3 and 20 mm at Baseline Visit and be located on hands, feet (excluding soles), limbs, and/or trunk. Flat, plantar, facial, periungual, genital warts or warts in region of pre-existing inflammatory condition are excluded from injection
- 4. Subjects enrolled into Cohort 3 must have common warts for injection in at least 2 different anatomic regions defined as: left arm, right arm, left hand, right hand, left leg, right leg, left foot (excluding sole), right foot (excluding sole) and torso
- 5. Subject, male or female is willing to use effective contraceptive method for at least 30 days before the Baseline Visit and at least 30 days after the last study drug administration unless not of childbearing potential as defined as post-menopausal for at least 2 years (females) or surgically sterile (tubal ligation, oophorectomy, or hysterectomy for females, and vasectomy for males). The only contraceptive usage exceptions would be individuals in exclusive same sex partnerships and individuals who agree to remain non-sexually active for the duration of the study. Acceptable contraceptive methods for subjects include:
 - Barrier methods such as condom, sponge or diaphragm combined with spermicide in foam, gel or cream;
 - b. Hormonal contraception (oral, intramuscular, implant or transdermal which includes Depo-Provera, Evra and Nuvaring);
 - c. Intrauterine device (IUD)

Female subjects of childbearing potential in a same sex partnership or who are abstinent will still receive pregnancy test as outlined in Appendix A.

6. Mentally and legally capable of giving informed consent prior to any study related procedures

